14	CONFLICT OF INTEREST POLICY	15
15	REFERENCES	17
16	ATTACHMENTS	17

CONFIDENTIAL

This material is the property of the NYU School of Medicine and Langone Medical Center. Do not disclose or use except as authorized in writing by the study sponsor

List of Abbreviations

AE	Adverse Event/Adverse Experience
CFR	Code of Federal Regulations
CRF	Case Report Form
CSOC	Clinical Study Oversight Committee
DCC	Data Coordinating Center
DHHS	Department of Health and Human Services
DSMB	Data and Safety Monitoring Board
FFR	Federal Financial Report
FWA	Federalwide Assurance
GCP	Good Clinical Practice
HIPAA	Health Insurance Portability and Accountability Act
ICF	Informed Consent Form
IRB	Institutional Review Board
ISM	Independent Safety Monitor
MOP	Manual of Procedures
N	Number (typically refers to participants)
NIH	National Institutes of Health
OHRP	Office for Human Research Protections
OHSR	Office of Human Subjects Research
PI	Principal Investigator
QA	Quality Assurance
QC	Quality Control
SAE	Serious Adverse Event/Serious Adverse Experience
SOP	Standard Operating Procedure
US	United States

CONFIDENTIAL

This material is the property of the NYU School of Medicine and Langone Medical Center. Do not disclose or use except as authorized in writing by the study sponsor

Protocol Summary

[figure not shown]
Title	Calcific Tendonitis Treatment-Barbotage vs. Barbotage with Cortisone Injection: A Randomized Controlled Double-Blind Study
Short Title	Calcific Tendonitis Treatment-Barbotage vs. Barbotage with Cortisone Injection
Protocol Number	S19-01299
Population	A sample size of 140 patients belonging to NYU Langone Health with calcific tendonitis will be enrolled including both genders, ages 18-90.
Objectives	The purpose of this study is to determine the efficacy of barbotage therapy by comparing the clinical and sonographic changes in patients that solely receive barbotage to patients receiving the standard of care, barbotage with cortisone injection.
Study Center(s)	Single-center, prospective study
Number of Subjects	We will aim to enroll a total of 140 subjects.
Study Duration	The estimated duration of the study is 24 months.
Subject Participation Duration	Each patient will be present for the day of treatment and follow-up at: 6 weeks, 3 months, and 6 months. Patients will be in the study for 6 months.
Estimated Time to Complete Enrollment	The estimated time to completion of enrollment is 24 months.
Statistical Methodology	Statistical analysis will be performed using ANOVA or t tests. Pearson's correlation will be used to determine relationship between outcomes scores.

CONFIDENTIAL

This material is the property of the NYU School of Medicine and Langone Medical Center. Do not disclose or use except as authorized in writing by the study sponsor

Drug/Device Template Version: 13 JUN 2016

Schematic of Study Design

CONFIDENTIAL

This material is the property of the NYU School of Medicine and Langone Medical Center. Do not disclose or use except as authorized in writing by the study sponsor

1 Introduction, Background Information and Scientific Rationale

1.1 ***Background Information and Relevant Literature***

Calcific tendonitis is a disorder characterized by pain and development of calcium deposits on one or more rotator cuff tendons and affecting normal sleeping habits and routine daily activities. Inflammation associated with the calcium deposit is theorized to contribute to the pain [1]. A few studies state the prevalence of the condition has been reported to be 3 to 10% in the general population [2, 3]. Several treatment modalities exist including anti-inflammatory and analgesic, extra-corporeal shockwave therapy (ESWT), ultrasound-guided needling and lavage (barbotage), and surgical treatment are in use. However, a consensus to which treatment is superior nor most effective does not exist.

1.2 ***Rationale***

Ultrasound-guided barbotage is a safe and efficient form of therapy for calcific tendonitis, with slightly more than half of the patients experiencing pain relief [4]. The procedure involves percutaneous insertion of a needle with saline, washing and aspirating the fluid content of the joint. By irrigating and aspirating the calcium deposit, symptomatic relief is achieved and signs of pathological resolution is seen on sonogram. All of this is achieved while preserving the native tendon, potentially avoiding surgery. Barbotage with cortisone injection continues to be the standard of care for calcific tendonitis resistant to physical therapy and cortisone injection, but it is not known if barbotage alone can provide the same amount of clinical and symptomatic resolution. We would like to evaluate and witness any significant difference from the standard treatment of care.

1.3 ***Potential Risks & Benefits***

1.3.1 ***Known Potential Risks***

Associated Risks of Cortisol Injection: Some of the reported side effects of cortisone injection are joint infection, nerve damage, thinning of the skin and soft tissue around the injection site, temporary flare of pain and inflammation after injection and whitening or lightening of the skin around the injection site.

Associated Risks of Not Receiving Cortisol: Temporary pain and potentially prolonged inflammation following barbotage treatment.

Associated Risks of X-Ray: During this study, subjects will have exposure to radiation from a shoulder x-ray. This radiation exposure is not necessary for their medical care and is for research purposes only. This means subjects will be exposed to small doses or amounts of radiation. The risk from this amount of radiation is less than the risk from everyday exposure to the sun. The risks of receiving very small doses of radiation are thought to be low. These risks are not actually known.

Female subjects must have a negative pregnancy test before they can have an X-ray. This will be administered at the 6-month visit before the x-ray.

Potential Loss of Confidentiality: While every effort will be made to keep subjects' information confidential, there is the potential risk of loss of confidentiality. In order to minimize this risk, any information that can identify a patient will be removed and replaced with a unique study ID that only the study coordinator/investigators will know.

Psychological Risks: When completing the questionnaires, subjects may come across a question or answer choice they find unpleasant, unsure on how to answer or otherwise objectionable. We will tell subjects there is no right or wrong answer to minimize this risk.

CONFIDENTIAL

This material is the property of the NYU School of Medicine and Langone Medical Center. Do not disclose or use except as authorized in writing by the study sponsor

1.3.2 Known Potential Benefits

We don't know if subjects will benefit from being in this study. There is a possibility the saline barbotage without cortisone may help some patients. However, we do not know for sure. We hope the results of this study will benefit future patients with this condition.

2 Objectives and Purpose

2.1 Primary Objective

The primary objective of the study is to determine the efficacy of barbotage without cortisone on patients with calcific tendonitis by measuring their clinical improvement via VAS, QuickDASH, and ASES Shoulder scores and radiographic size of calcium deposit.

3 Study Design and Endpoints

3.1 Description of Study Design

This will be a single-center, prospective, randomized study. This study will determine patient outcomes after minimally invasive treatment to determine the efficacy of barbotage therapy on patients with calcific tendonitis.

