3.2 Study Endpoints

3.2.1 Primary Study Endpoints

The primary study endpoint will focus on the decrease in pain of the affected shoulder measured by VAS scores. Based on their responses and their scores at the time prior to and after their barbotage therapy begins, we can determine a primary endpoint with a 10% change between baseline and their final visit. We would also like to observe the affected rotator cuff tendon and measure the efficacy of barbotage therapy via shoulder radiograph. Shoulder X-Ray is considered standard of care and we expect a resolution in size of the calcified deposit by at least 10% after aspiration and lavage.

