5.1 Study Procedures/Evaluations

Once the study team member arrives to the physician office, they will provide the potential patient subjects with information on the study and ask the patient for their consent to be in the study. The patient will be given shoulder-related questionnaires (ASES and QuickDASH), asked to complete a VAS survey and will receive a shoulder radiograph prior to treatment and at 6 months post-treatment, to evaluate the state of the condition.

Patients in this study will receive the assigned form of treatment and have assigned follow-up appointments at 6 weeks, 3 months and 6 months post-treatment. The alternative treatment (barbotage with saline injection) will be administered in the same fashion as the control (barbotage with cortisone injection). If the patient desired to solely have the standard therapy, they will be ineligible for the study.

Patients will be randomized to one of two cohorts: receiving barbotage with saline injection or receiving barbotage with cortisone injection. Both groups will follow the same protocol for standard of care: 4 mg of dexamethasone (if receiving cortisone) and barbotage. Cortisone dosing is consistent with FDA-approved guidelines. The saline used for the barbotage and sham injection are the same, and readily available in the procedure room. The saline is manufactured by B. Braun Medical, available in the procedural room, and will be equivalent in volume to that of the cortisone injection, determined by the performing physician. [name] will be performing the procedure. At each follow-up appointment, the patients will complete the questionnaires and VAS scores. Patients and physicians will be blinded to the cohort; patients will be randomly chosen by the research study members excluding the primary investigator (PI). The barbotage

CONFIDENTIAL

This material is the property of the NYU School of Medicine and Langone Medical Center. Do not disclose or use except as authorized in writing by the study sponsor

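### Sections 2.1, 3.1 and 3.2.1 state the aim as the efficacy of barbotage, which both arms receive; the wording should match the between-arm comparison that the design can deliver

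*Combined protocol and SAP*

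**What the plan says.** The aim is worded in two ways.

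- **With a comparison.** The title sets barbotage against barbotage with cortisone. The Protocol Summary (Objectives) intends to "determine the efficacy of barbotage therapy by comparing the clinical and sonographic changes in patients that solely receive barbotage" with changes in patients given the standard of care, barbotage with cortisone. Section 1.2 gives the open question: "it is not known if barbotage alone can provide the same amount of clinical and symptomatic resolution".
- **Without a comparison.** Section 2.1: "The primary objective of the study is to determine the efficacy of barbotage without cortisone on patients with calcific tendonitis". Section 3.1: "This study will determine patient outcomes after minimally invasive treatment to determine the efficacy of barbotage therapy on patients with calcific tendonitis". Section 3.2.1, on imaging: "We would also like to observe the affected rotator cuff tendon and measure the efficacy of barbotage therapy via shoulder radiograph".

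On treatment, section 5.1 says "Patients will be randomized to one of two cohorts: receiving barbotage with saline injection or receiving barbotage with cortisone injection", and "Both groups will follow the same protocol for standard of care: 4 mg of dexamethasone (if receiving cortisone) and barbotage". The arm with cortisone is the control.

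Sections 3.2.1 and 3.2.2 define the endpoints (VAS; ASES and QuickDASH) as a 10% change from baseline to the final visit. Section 3.2.1 also expects the deposit to shrink by at least 10% following aspiration and lavage. Section 8.1 names paired t-tests for roughly normal continuous variables, Mann-Whitney otherwise, and chi-squared or Fisher tests for binary variables. The Protocol Summary names ANOVA or t tests.

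**The concern.** To show that barbotage is effective, a trial must compare patients who have it with patients who do not. Here everyone has it. Improvement within an arm mixes barbotage with the natural course of the condition, regression to the mean, response to the procedure and sham injection, and any other care. The between-arm difference removes those shared components, and it removes barbotage with them.

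What is at stake is the conclusion. If both arms improve, the wording in 2.1, 3.1 and 3.2.1 invites a statement that barbotage works, with no control behind it. If the arms do not differ, that tells the reader nothing about whether barbotage works and, without a margin, does not show that the arms are equivalent.

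**Working it through.** The plan gives no figure for this point, and its sample-size figure in 8.1 is not an input to steps 1 to 3.

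**1. Arms against objective.** Section 5.1 has two arms, barbotage with saline injection and barbotage with cortisone injection. There is no sham barbotage, no injection without barbotage and no untreated arm. The only randomised difference is steroid versus saline.

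**2. What each contrast estimates.** Let *N* be the improvement that would occur without barbotage or steroid (natural course, regression, sham response, other care), *B* the barbotage effect, and *S* the effect of adding the steroid to barbotage.

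- Saline arm, mean change: *N + B*
- Cortisone arm, mean change: *N + B + S*
- Between-arm difference: (*N + B + S*) − (*N + B*) = *S*

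If the steroid acts differently with and without barbotage, *S* is simply its effect in the presence of barbotage. The difference still does not identify *B*.

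Assumed values, for illustration only: *N* = 1 SD, *S* = 0.5 SD.

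- *B* = 0: saline-arm change 1 + 0 = 1 SD; difference 0.5 SD
- *B* = 1: saline-arm change 1 + 1 = 2 SD; difference 0.5 SD
- *B* = 2: saline-arm change 1 + 2 = 3 SD; difference 0.5 SD

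A simulation with 64 per arm and 4,000 repeats agreed: differences 0.499, 0.497 and 0.498 SD, and saline-arm changes 0.998, 2.003 and 3.002 SD. With *B* = 0 the saline arm still improves by a full SD.

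**3. Which contrast the endpoints and tests point to.** The 10% criteria in 3.2.1 and 3.2.2 are within-patient changes. A paired t-test in a trial of unmatched arms is naturally a before-after test, whereas Mann-Whitney, its stated fallback, compares independent groups. So 8.1 mixes the two, and nothing ties a between-arm test to the primary objective. For imaging, aspiration and lavage are common to both arms. A between-arm comparison of deposit change is valid, but it tests the steroid and not the lavage.

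**4. If the intended conclusion is similarity (1.2).** The plan states no margin. Assume one-sided alpha 0.025, power 0.80 and no true difference. For a margin of *m* SD, the number per arm is 2(1.960 + 0.842)²/*m*² ≈ 15.70/*m*², rounded up.

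- *m* = 0.3: 175 per arm, 350 in total
- *m* = 0.4: 99 per arm, 198 in total
- *m* = 0.5: 63 per arm, 126 in total
- *m* = 0.6: 44 per arm, 88 in total

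These totals are before dropout. Conversely, the planned 140 at 1:1 is 70 per arm, which supports a margin of 2.802 × √(2/70) ≈ 0.47 SD. If the 10 per group allowed for loss are all lost, 60 per arm supports 2.802 × √(2/60) ≈ 0.51 SD.

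**The case against.** The strongest reply is that the trial is comparative and the rest is loose drafting. The Summary's objective, read to its end, names both arms and the comparison. The title does the same, and 1.2 asks whether barbotage alone matches standard care while treating barbotage itself as already established. Section 2.1 specifies barbotage *without cortisone*, which hints at the contrast. In 8.1 the per-group sizing, the chi-squared or Fisher tests and Mann-Whitney all fit a between-arm analysis. No section states a rule that barbotage will be declared effective if patients improve.

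Much of this stands. The two-arm design suits the comparative question, and a reader should not infer that the plan commits itself to an uncontrolled efficacy conclusion; it only leaves room for one.

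The mismatch remains for three reasons. The formal primary objective in 2.1 names no comparator, and the Summary presents the comparison as the means of determining barbotage efficacy, which adding a steroid to a shared procedure cannot do. The endpoints follow the efficacy wording, not the comparison. Nor does an active-control argument fill the gap: inferring efficacy from similarity to standard care needs a margin and evidence that the control works, and 1.2 offers only that slightly more than half of patients get pain relief.

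**Conclusion.** The point holds as a mismatch between the wording of the objective and endpoints and a design that is otherwise able to answer the comparative question. The randomised contrast carries no information on the effect of barbotage, whatever its size. That follows from the arms in 5.1 and does not depend on the illustrative values.

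Two stronger readings are tempting and unsupported. One is that the trial is wrongly designed and needs an arm without barbotage. That would follow only if the efficacy of barbotage itself were the intended question, and the title, Summary and Rationale indicate otherwise. The other is that regression to the mean alone would meet the 10% criterion. The documents cannot size it: section 4.1 requires three or more months of pain but sets no minimum VAS, and no population mean or test-retest correlation is given.

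**What to change.** - **Sections 2.1 and 3.1, and the opening words of the Summary objective:** restate the objective as estimating the between-arm difference (barbotage plus saline versus barbotage plus cortisone) in change in VAS from baseline to 6 months. Keep radiographic deposit size, QuickDASH and ASES as outcomes.
- **Section 3.2.1:** replace the sentence on measuring barbotage efficacy by radiograph with a between-arm comparison of change in deposit size. Add that within-arm change from baseline is descriptive and will not be reported as efficacy of barbotage.
- **Section 8.1:** tie a between-arm test to the restated primary objective.
- **If the sponsor wants to conclude that barbotage alone does as well as standard care:** state a margin with its justification in advance and check the sample size against it. A non-significant difference will not support that conclusion.

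The first three changes need no new patients, visits or arms. The trial gives up only a claim that it could not support. The fourth could raise the sample size, depending on the margin chosen.

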3.2 Study Endpoints

3.2.1 Primary Study Endpoints

The primary study endpoint will focus on the decrease in pain of the affected shoulder measured by VAS scores. Based on their responses and their scores at the time prior to and after their barbotage therapy begins, we can determine a primary endpoint with a 10% change between baseline and their final visit. We would also like to observe the affected rotator cuff tendon and measure the efficacy of barbotage therapy via shoulder radiograph. Shoulder X-Ray is considered standard of care and we expect a resolution in size of the calcified deposit by at least 10% after aspiration and lavage.

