4.2 Exclusion Criteria

An individual who meets any of the following criteria will be excluded from participation in this study:

- Legally incompetent or mentally impaired (e.g. minors, Alzheimer's subjects, dementia, etc.)
- Osteoarthritis of the glenohumeral joint of the affected shoulder
- Previous surgery or barbotage to the affected shoulder
- History of prior allergic/hypersensitivity reactions related to the study medication
- Shoulder instability, glenohumeral arthritis, AC pathology, inflammatory arthropathy, fibromyalgia, frozen shoulder or cervical radiculopathy
- Sub-acromial injection with a corticosteroid or treatment by ESWT during the last 3 months before inclusion
- Younger than 18 years of age or older than 90
- Any patient considered a vulnerable subject

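### Further treatment of the study shoulder after Day 0 has no handling rule in the month-6 VAS comparison, and ESWT, repeat barbotage and surgery have no named data item

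*Combined protocol and SAP*

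**What the plan says.** **Question and endpoint.** Section 2.1 sets out to "determine the efficacy of barbotage without cortisone on patients with calcific tendonitis". Section 1.2 gives the reason: "it is not known if barbotage alone can provide the same amount of clinical and symptomatic resolution". The arms in 5.1 are patients "receiving barbotage with saline injection or receiving barbotage with cortisone injection". For the primary endpoint, 3.2.1 says "The primary study endpoint will focus on the decrease in pain of the affected shoulder measured by VAS scores" and adds that "we can determine a primary endpoint with a 10% change between baseline and their final visit". The final visit is at the end of month 6 (5.2.4).

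**Other treatment of the shoulder.** It is mentioned only as a reason not to enrol. Section 4.2 excludes "Sub-acromial injection with a corticosteroid or treatment by ESWT during the last 3 months before inclusion" and "Previous surgery or barbotage to the affected shoulder". No section permits, prohibits or defines these treatments after Day 0.

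**Data collected after Day 0.** Section 5.1 says "At each follow-up appointment, the patients will complete the questionnaires and VAS scores". Section 5.2.3 lists only the visit and VAS. Section 5.2.4 lists VAS, ASES, QuickDASH and the radiograph. Attachment A has no row for further shoulder treatment; its Subject Survey, at Visit 1 and the final session, is not described. Section 12.1 names concomitant medications among the data entered in REDCap. Section 6.3 has AEs asked about at each visit and treats deterioration as an AE.

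**Analysis and departures.** Section 8.1 names tests but no analysis population and no rule for later treatment. Section 4.7.1 lets the investigator terminate a participant who newly meets an exclusion criterion that rules out continuing. Section 4.7.2, whose heading covers withdrawal and termination, removes the data of patients who withdraw and enrols a replacement.

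**The concern.** Patients enter with at least 3 months of pain, after physical therapy and cortisone have failed, and with the intention of having barbotage with cortisone (4.1). They are then followed for 6 months, long enough for some to receive more treatment. Section 1.3.1 lists temporary pain and possibly prolonged inflammation as risks of omitting cortisone, so more rescue on saline is plausible, though not certain.

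A later steroid injection in a saline patient resembles the comparator treatment. If that patient's month-6 VAS is analysed without comment, the saline result includes treatment that the objective meant to exclude. If the patient is instead removed and replaced, the saline arm loses someone still in pain. When rescue is commoner on saline, both routes bring the arms together. A finding of no difference could then mean that barbotage alone suffices, or that it suffices with later treatment where needed.

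**Working it through.** **1. What happens to a rescued patient under the text**

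| Further treatment | Place for the data | Possible exit under 4.7.1 | Rule for month-6 VAS |
|---|---|---|---|
| Steroid injection | Concomitant medications (12.1) | Weak: criterion is tied to the time before inclusion | None |
| ESWT | No named item | Weak, same reason | None |
| Repeat barbotage | No named item | Unclear: every patient has barbotage on Day 0 | None |
| Surgery | No named item | Most plausible | None |

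The AE route in 6.3 could pick up treatment for a worsening shoulder. An outpatient procedure for pain that persists without worsening fits neither that route nor the medication field.

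**2. The plan's sample-size figure**

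Section 8.1 gives more than 128 patients for d = 0.6, power 0.80, alpha 0.05. A two-sided two-sample t-test needs 45 per arm (90 in total) at d = 0.6, and 64 per arm (128 in total) at d = 0.5. The stated total therefore matches d = 0.5. That is a separate matter; it is used here only to justify showing both values.

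**3. Illustration if rescued patients are counted as allocated**

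Inputs: 140 less 20 for losses (8.1) gives 120, or 60 per arm. SE = sqrt(2/60) = 0.1826. Assumptions: D is the saline-minus-cortisone difference in rescue rate; f is the share of the arm difference that rescue gives back; the SD is unchanged. Then d = d0(1 − f·D) and power = Φ(d/SE − 1.96).

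| d0 | f | D = 0 | D = 0.10 | D = 0.20 | D = 0.30 |
|---|---|---|---|---|---|
| 0.6 | 0.5 | 0.91 | 0.88 | 0.84 | 0.80 |
| 0.6 | 1 | 0.91 | 0.84 | 0.75 | 0.63 |
| 0.5 | 0.5 | 0.78 | 0.74 | 0.69 | 0.64 |

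Example: d0 = 0.6, f = 0.5, D = 0.20 gives d = 0.6 × 0.90 = 0.54, and Φ(0.54/0.1826 − 1.96) = 0.84.

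All patients had already failed cortisone, which argues for f below 1 for a steroid injection. Nothing in the documents limits f to 1 for surgery or repeat barbotage.

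**4. Illustration if rescued patients are deleted and replaced**

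An extreme assumption is made here: the deleted share r of an arm is exactly those with the worst month-3 VAS, and month-3 and month-6 scores correlate 0.5. With z = Φ⁻¹(1 − r) and L = φ(z)/(1 − r), the arm mean improves by 0.5L SD and its variance becomes 1 − 0.25(zL + L²). For r = 5%, 10% and 20% the shifts are 0.054, 0.097 and 0.175.

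| Deleted, saline v cortisone | Difference (from 0.6) | SE | Power |
|---|---|---|---|
| 5% v 0% | 0.546 | 0.180 | 0.86 |
| 10% v 5% | 0.557 | 0.177 | 0.88 |
| 20% v 10% | 0.523 | 0.174 | 0.85 |
| 20% v 0% | 0.425 | 0.178 | 0.67 |

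Equal rates shift both arms equally and give no bias.

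**5. What recording would show**

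Suppose 15/60 are rescued on saline and 6/60 on cortisone. The difference is 25% − 10% = 15 points, SE = sqrt(0.25 × 0.75/60 + 0.10 × 0.90/60) = 0.068, and the 95% CI is 15 ± 13.3, or 1.7 to 28.3 points. Counting those patients as not improved would move a responder-rate difference by up to the same 15 points, if all would otherwise have counted as improved. The 95% half-width of that difference, 1.96·sqrt(2p(1 − p)/60), is 14.3 points at p = 0.8 and 17.9 at p = 0.5.

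**The case against.** **Capture may be better than the protocol shows.** The CRF and manual of procedures are not among the documents, and the Subject Survey's content is unknown. The trial is single-centre, and hospital and office charts are given as examples of source documents (section 9). A reader might infer that none of the four treatments is recorded. The documents do not support that: 12.1 covers steroid injections, and procedures done at the site could be traced. What stands is that ESWT, repeat barbotage and surgery have no named item, and treatment elsewhere could be missed.

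**Counting as allocated is a sound default.** It is also the primary analysis recommended here, so a reader who takes the power losses in step 3 as the gain from the fix would be wrong. They describe dilution that remains after it. In the case closest to the stated plan (d = 0.6, f = 0.5), power is still 0.80 with a 30-point imbalance.

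**Deletion is discretionary.** Section 4.7.1 says that the investigator may terminate, and the operative sentence of 4.7.2 speaks of patients who withdraw. It would be too strong to say that rescued patients will be deleted. The text leaves the route open, most plausibly after surgery.

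**Blinding does not settle the cause.** A reader might infer that excess rescue on saline must reflect pain, since patients and the PI are blinded. The proceduralist and study team are not (5.1, 8.2.1), so that does not follow.

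**The plan tests for a difference.** Section 1.2 also speaks of looking for a significant difference, and there is no equivalence margin. This is correct, but its stated uncertainty is whether barbotage alone achieves as much, so a null result is likely to be read as an answer.

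**Conclusion.** The point holds in a limited form. The plan has no rule for further corticosteroid, ESWT, repeat barbotage or surgery after Day 0 in the month-6 VAS comparison. Three of the four have no named item, and the exit and replacement rules could remove rescued patients at discretion. It is worth correcting before data accrue, because procedures not recorded prospectively may not be reliably recovered.

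The size is unknown. Bias requires unequal rescue between arms, and the documents give no rate. Under the assumptions shown, counting rescued patients as allocated costs little to moderate power: 0.91 falls to between 0.80 and 0.63 at a 30-point excess with d = 0.6. The deletion figures rest on a stronger assumption and should carry less weight. The firmer consequence is for interpretation: without rescue shown by arm, a null result cannot be attributed to barbotage alone. Confidence is medium, and the change is advisable rather than essential.

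**What to change.** Leave clinical care to the treating physician and change only recording and handling.

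1. At week 6, month 3 and month 6, record any corticosteroid, ESWT, repeat barbotage or surgery to the study shoulder, with its date. Take VAS before any such treatment given at that visit.
2. Amend 4.7.1 and 4.7.2 so that such treatment does not lead to termination, data removal or replacement.
3. State in 8.1 that all randomised patients are analysed as allocated, and report further treatment by arm beside the primary result.
4. Add one supplementary analysis. Either use the last VAS before rescue, or count rescued patients as not achieving the 10% VAS decrease once 3.2.1 defines that per patient. Word any conclusion about barbotage alone accordingly.

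The cost is one CRF item at three existing visits, a short amendment and one extra analysis. The as-allocated estimate still contains any dilution. The last-VAS version mixes assessment times (a patient rescued before week 6 contributes only baseline), so the supplementary analysis can only support the primary result.

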5.2.4 Final Study Visit

Final Study Visit (End of Month 6)

- Record VAS, ASES Shoulder, and QuickDASH scores.
- Perform Shoulder Series X-Ray for Research Purposes

CONFIDENTIAL

This material is the property of the NYU School of Medicine and Langone Medical Center. Do not disclose or use except as authorized in writing by the study sponsor

6 Assessment of Safety

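### The primary VAS endpoint is a 10% change from baseline with no arm contrast, and with normal data section 8.1 tests it within patients rather than between arms

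*Combined protocol and SAP*

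**What the plan says.** Section 3.2.1 opens with "The primary study endpoint will focus on the decrease in pain of the affected shoulder measured by VAS scores" and continues "we can determine a primary endpoint with a 10% change between baseline and their final visit". The final visit is at Month 6 (section 5.2.4). Under the same heading the protocol adds, in softer terms, that the team would like to look at the tendon on X-ray, and that "we expect a resolution in size of the calcified deposit by at least 10% after aspiration and lavage". Section 3.2.2 repeats the 10% sentence, including the words for a primary endpoint, for ASES and QuickDASH. Section 2.1 describes the primary objective as "measuring their clinical improvement via VAS, QuickDASH, and ASES Shoulder scores and radiographic size of calcium deposit", without ranking the four measures.

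The Protocol Summary gives the purpose as "comparing the clinical and sonographic changes in patients that solely receive barbotage to patients receiving the standard of care". On methods it says "Statistical analysis will be performed using ANOVA or t tests", without saying what is compared with what. Section 8.1 assigns tests by type of variable: chi-squared or Fisher for binary data, a paired t-test for continuous data that are close to normal, and Mann-Whitney otherwise. It does not say which type the primary endpoint is, and it ties its effect size to no outcome.

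**The concern.** The endpoint sentence describes change over time, whereas the trial's question is about a difference between arms. Both arms receive barbotage (section 5.1), so a 10% improvement from baseline can occur in both whether or not cortisone adds anything.

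Section 8.1 does not repair this. Nothing in the 1:1 parallel-group design pairs a patient in one arm with a patient in the other. The only pairing available is a patient's own baseline and follow-up, so the paired t-test answers whether patients changed. Mann-Whitney compares independent groups, so it answers whether the arms differ. The shape of the data would therefore decide which question is answered. If the 10% is a rule for each patient, the endpoint is binary and a third route applies, with a loss of power.

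**Working it through.** **The routes in section 8.1, side by side**

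| Reading of the VAS endpoint | Test under 8.1 | Question answered |
|---|---|---|
| Continuous, normal | Paired t-test | Did patients change from baseline? |
| Continuous, not normal | Mann-Whitney | Do the arms differ? |
| Responder (10% per patient) | Chi-squared or Fisher | Do response rates differ by arm? |

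Only the second and third match the Summary's objective.

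**Inputs.** Section 8.1 gives d=0.6, power 0.80, alpha 0.05 (taken here as two-sided), more than 128 patients required, 140 enrolled, and 10 per group for losses. Evaluable patients: 140 − 20 = 120, or 60 per arm.

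**The plan's own figure.** For a two-sample t-test at 80% power, d=0.6 needs 44.6, so 45 per arm (90 in total). d=0.5 needs 63.8, so 64 per arm (128 in total). The stated 128 thus matches d=0.5, not d=0.6. That is a separate sample-size matter; it is used here only to explain why both values of d are shown.

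**Within-arm reading.** Assume identical arms, 60 patients each, and a paired t-test in each arm. With e = mean change ÷ SD of change, the noncentrality is e × √60 on 59 degrees of freedom. The arms are independent, so the probability that both tests are significant is the per-arm power squared. The documents give no value for e, so three are assumed.

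| e | e × √60 | Power per arm | Both arms significant |
|---|---|---|---|
| 0.3 | 2.32 | 0.628 | 0.628² = 0.394 |
| 0.5 | 3.87 | 0.968 | 0.968² = 0.937 |
| 0.8 | 6.20 | >0.999 | >0.999 |

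A between-arm test at 0.05 would be significant in 5% of such trials.

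**Responder reading.** Let p be the response rate in the worse arm. A normal shift of d gives the other arm Φ(Φ⁻¹(p) + d). Power is for the uncorrected chi-squared test by exact enumeration, at 60 per arm. The comparator is the two-sample t-test with noncentrality d × √(60/2): 0.6 × √30 = 3.29 gives power 0.903, and 0.5 × √30 = 2.74 gives 0.775.

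| p (assumed) | Other arm, d=0.6 | Power, d=0.6 | Other arm, d=0.5 | Power, d=0.5 |
|---|---|---|---|---|
| 50% | 72.6% | 73% | 69.1% | 58% |
| 70% | 87.0% | 63% | 84.7% | 50% |
| 80% | 92.5% | 52% | 91.0% | 40% |
| 90% | 97.0% | 34% | 96.3% | 27% |
| Continuous VAS, t-test | | 90% | | 78% |

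The protocol's only figure on response is in section 1.2, "slightly more than half of the patients experiencing pain relief". It is not tied to a 10% threshold, so p is shown as a range.

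**The case against.** The strongest reply is that a between-arm comparison is plainly meant. The title sets one treatment against the other, the Summary's objective compares them, section 1.2 looks for a difference from standard care, the allowance for losses is per group, and Mann-Whitney and chi-squared compare independent groups. On this view, paired is a slip for unpaired. That is plausible, and it rules out the reading that the trial has no between-arm question. It does not rescue the text: if paired is a slip, the named test is wrong and must be corrected, and the 10% is still undefined. It does mean that the within-arm probabilities are an illustration. No section says that success means two significant paired tests.

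A reader might also infer that VAS and X-ray are co-primary and that the type I error is therefore inflated. The documents do not support this. Section 3.2.1 names the primary endpoint in the singular as VAS pain, the X-ray wording is weaker, and no section lets success on either outcome count or requires both. What stands is that deposit size appears under a plural primary heading with no stated status. The primary wording in section 3.2.2 is probably a copied sentence, since it sits under a clear secondary heading.

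Finally, baseline adjustment is a choice. An unadjusted two-sample comparison of change would also restore the contrast.

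**Conclusion.** The point holds as a fault in the definition of the endpoint and in the choice of test, not in the trial's intent. Followed literally with normal data, section 8.1 does not test the comparison that the Summary sets as the objective. This conclusion rests on the text alone.

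The sizes are conditional. The within-arm figures (39%, 94%, over 99%) assume identical arms and changes of 0.3 to 0.8 SD. The responder figures assume a normal shift and response rates of 50% to 90% in the worse arm. Over that range the loss against continuous VAS at 60 per arm is 90 − 73 = 17 to 90 − 34 = 56 percentage points at d=0.6, and 78 − 58 = 20 to 78 − 27 = 51 at d=0.5. Continuous VAS does not itself secure 80% in every case: at d=0.5 and 60 per arm the unadjusted t-test has 78%.

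The sponsor should correct this before anyone sees data by arm, so that the choice among readings cannot depend on the results.

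**What to change.** - In section 3.2.1, state the primary endpoint as the between-arm difference in VAS pain at 6 months.
- In section 8.1, replace the paired t-test for this comparison with a between-arm analysis of continuous VAS with baseline VAS as covariate, at two-sided 0.05. Align the Summary's methods line with it.
- Define the 10% (relative or absolute, and per patient if so meant) and report the proportions reaching it by arm, descriptively.
- State that X-ray deposit size is not primary. If the sponsor wants it primary, state the rule for success and restate power.
- Rank the measures in section 2.1 to match, and correct the primary wording in section 3.2.2.

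The cost is an amendment with IRB approval (section 11.2). No visit or measurement is added, because VAS is already recorded at baseline and Month 6. The X-ray would lose any claim to primary status. One limit remains: a difference test that is not significant does not show that barbotage alone gives as much relief, which is how section 1.2 frames the question. That is a separate decision for the sponsor.
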